## 8.2. Secondary Efficacy Analyses (From HRCT Analyses)

### 8.2.1. Endpoint / Variables

To evaluate the effect of once daily repeat inhaled doses of nemiralisib on lung parameters derived from HRCT scans in subjects with acute exacerbation of COPD, compared to placebo. Ratio from baseline in siVaw, iVaw, iRaw, siRaw, trachea length and diameter at FRC and TLC after 12 days of treatment and after 28 days of treatment.

### 8.2.2. Summary Measure

Each HRCT scan will be conducted at two lung volumes: total lung capacity (TLC) and functional residual capacity (FRC); these will be referred to as scan conditions. The HRCT images will be processed to derive the HRCT parameters at FRC and TLC, however these conditions are not applicable for all parameters.

The HRCT scans will be conducted at Screening, Day 12 and Day 28. The 3 HRCT images will then be processed to derive the HRCT parameters at each scan; this data will be referred to as the untrimmed data. The untrimmed data measures all airways that are present in each scan.

However partially due to positioning of subjects whilst taking a scan, it can be that some airways are visible in some scans and not in other scans. For these reasons, some HRCT

imaging endpoints will be calculated to include only airways that are visible in both scans. Therefore, the scans were grouped into three scan trimming pairs where, within each scan trimming pair, the airways that were not present in both scans were removed/trimmed.

The three scan trimming pairs, and subsequent timepoints, are:

- The scan trimming pair SCRD28, which contains the Screening (SCRD28:SCR) and Day 28 (SCRD28:D28) timepoints, where only airways that were present in both screening and day 28 scans are accounted for.
- The scan trimming pair SCRD12, which contains the Screening (SCRD12:SCR) and Day 12 (SCRD12:D12) timepoints where only airways that were present in both screening and day 12 scan are accounted for.
- The scan trimming pair (D12D28), which contains the Day 12 (D12D28:D12) and Day 28 (D12D28:D28) timepoints, where only airways that were present in both day 12 and day 28 scans are accounted for.

These 6 HRCT images were then processed to derive the HRCT parameters at each of these scan-trimming pair time points; this data will be referred to as the scan trimmed data. The scan trimmed data considers only airways that were present in both scans within the scan trimming pair. This ensures the airway models are the same length although the cross-sectional area of the airway may vary. For example, the schematic below shows visible airways on Screening alone and Day 12 alone. It then shows the airways that are visible on both Screening & Day 12 scans, through removing/trimming airways that are not present in both scans.

The HRCT scans can identify the 5 different lobes of the lungs and these lobes can then be categorized into and up to 5 regions depending on the endpoint. The 5 lobes are Right Upper Lobe (RUL), Left Upper Lobe (LUL), Right Middle Lobe (RML), Right Lower Lobe (RLL) and Left Lower Lobe (LLL). The 5 regions are Upper (comprising of RUL, RML and LUL), Lower (comprising of RLL and LLL), Central (the main bronchi between the lobes and the trachea), Distal (comprising of Upper and Lower) and Total (comprising of Distal and Central).

The endpoints for which the 5 regions apply include:

- Specific imaging airway volume (siVaw)
- Imaging airway volume (iVaw)
- Specific imaging airway resistance (siRaw)
- Imaging airway resistance (iRaw)
- Specific imaging airway wall volume (siVaww)
- Imaging airway wall volume (iVaww)

The endpoints for which only 3 regions (upper, lower & total) apply include:

- Imaging lobe volume (iVlobe)
- Percent predicted lobar volume (iVlobepred)
- Low attenuation score (LAS)
- Air trapping score (AT)
- Blood vessel density (BVD)

The endpoint for which only 2 regions (upper & lower) apply is:

- Internal airflow lobar distribution (IALD)

For the measures iVaw, iRaw and iVaww, standardization within a subject for the size of the lobar volume was conducted. These specific measures can be adjusted for the individual's lobar volume by correcting for the corresponding lobe/region. Note the central region is not applicable for lobar volumes, instead the corresponding region for the central, distal and total regions is the total lobar volume region. For example:

- To calculate siVaw, the lobes/regions of iVaw being divided by the corresponding lobes/regions of iVlobe to calculate the lobes/regions of siVaw, thus siVaw can be defined as a measure of volume in an individual's airways, corrected for the individual's lobar volume.
- To calculate siRaw, the lobes/regions of iRaw were multiplied by the corresponding lobes/regions of iVlobe.
- To calculate siVaww, the lobes/regions of iVaww were divided by the corresponding lobes/regions of iVlobe.

For such reasons, the table below shows the HRCT endpoints and the results that will be captured:

**Table 2 HRCT Endpoints (and results that will be captured)**

Endpoints	Units	Untrimmed			Scan Trimming, based on:		
		Screening	Day 12	Day 28	Screening and Day 12 scans	Screening and Day 28 scans	Day 12 and Day 28 scans
iVaw	mL	x	x	x	x (Screening) x (Day 12)	x (Screening) x (Day 28)	x (Day 12) x (Day 28)
siVaw	mL/L	x	x	x	x (Screening) x (Day 12)	x (Screening) x (Day 28)	x (Day 12) x (Day 28)
iRaw	KPa*s/L				x (Screening) x (Day 12)	x (Screening) x (Day 28)	x (Day 12) x (Day 28)
siRaw	KPa*s				x (Screening) x (Day 12)	x (Screening) x (Day 28)	x (Day 12) x (Day 28)
iVlobe	L	x	x	x			
Percent Predicted iVlobe	% of Predicted value	x	x	x			
IALD 	%	x	x	x			
LAS 	% of iVlobe	x	x	x			
AT 	% of iVlobe	x	x	x			
BVD 	% of iVlobe	x	x	x			
iVaww 	mL	x	x	x	x (Screening) x (Day 12)	x (Screening) x (Day 28)	x (Day 12) x (Day 28)
siVaww 	mL/L	x	x	x	x (Screening) x (Day 12)	x (Screening) x (Day 28)	x (Day 12) x (Day 28)
Trachea length	mm	x	x	x			
Trachea Diameter	mm	x	x	x			
Trachea Length/Diameter	mm/mm	x	x	x			

All these endpoints will be measured at TLC and FRC, except:

[1] These endpoints will only be measured at TLC

[2] This endpoint will be measured only at FRC

[3] The state (TLC/FRC) is not applicable

For the endpoints siVaw, iVaw, iRaw and siRaw appropriate transformations will be applied prior to summaries and statistical analyses, likely a log transformation. Summary statistics will be presented for absolute data and change from baseline. An attempt will be made to fit separate statistical models for each endpoint, scan trimming condition (Untrimmed or Scan Trimmed), lung volume (FRC or TLC) and Lobes (RUL, LUL, RML, RLL and LLL) or Regions (Upper, Lower, Central, Distal and Total) combination as appropriate. The primary plan for statistical analyses will be to fit separate statistical models for:

- siVaw
  - Untrimmed at FRC for all lobes, i.e. RUL, LUL, RML, RLL and LLL in one model.
  - Untrimmed at FRC for all regions, i.e. Upper, Lower, Central, Distal and Total in one model.
  - Scan Trimmed at FRC for Distal region only.
- siRaw
  - Scan Trimmed at FRC for Distal region only.

For untrimmed data, the ratio from baseline across the different Regions (accounting for the average baseline associated to the Region of interest) will be represented via adjusted posterior medians for each of the Treatment Arms, as well as their associated 95% HPD-tailed credible intervals. These results will be presented within tabular form, and will be presented after the data have been appropriately back transformed (if applicable). In addition, the placebo-adjusted ratio from baseline across the different Regions will be represented via adjusted posterior medians, as well as their associated 95% HPD-tailed credible intervals and posterior probabilities. These results will be presented in tabular form, and will be presented after the data have been appropriately back transformed to give median ratios (or median differences if applicable).

For scan trimmed data, the change from baseline across the different Regions (accounting for the average baseline associated to the Region of interest) will be represented via adjusted posterior medians for each of the Treatment Arms, as well as their associated 95% HPD-tailed credible intervals. These results will be presented within tabular form, and will be presented after the data have been appropriately back transformed (if applicable). In addition, the placebo-adjusted change from baseline across the different Regions will be represented via adjusted posterior medians, as well as their associated 95% HPD-tailed credible intervals and posterior probabilities. These results will be presented in tabular form, and will be presented after the data have been appropriately back transformed to give median ratios (or median differences if applicable).

For the tracheal endpoints, absolute data and change from baseline summary statistics will be provided for each lung volume (FRC or TLC) for trachea length, diameter and length/diameter.

### **8.2.3. Population of Interest**

The primary efficacy analyses will be based on the “All Subjects” population, unless otherwise specified.

**8.2.4. Statistical Analyses / Methods**

Details of the planned displays are provided in [Appendix 10: List of Data Displays](#) and will be based on GSK Data Standards and statistical principles.

Unless otherwise specified, endpoints / variables defined in Section 8.2.1 will be summarised using descriptive statistics, graphically presented (where appropriate) and listed.

**8.2.4.1. Statistical Methodology Specification**

NOTE: The description below describes the current thinking of how to analyse these endpoints. The proposed models will be assessed, and if not appropriate alternative models could be used.

Endpoint / Variables

 
Imaging Untrimmed endpoint siVaw at FRC
 

Model Specification



Visits will be represented via adjusted medians, as well as their associated 95% HPD-tailed credible intervals. These results will also be presented within tabular form, and will be presented after the data have been appropriately back transformed (if applicable)
 
 
The probabilities that the treatment ratio is greater than 1 (depending on direction of the endpoint), in addition to other values appropriately selected based on the data, will also be computed for each Visit. These results will be presented in tabular format
 


Model Checking & Diagnostics
 
 
Model assumptions will be applied, but appropriate adjustments maybe made based on the data. For example, if data do not approximately follow a normal distribution then attempt will be made to find a suitable transformation.                      Note: Should parameters require a log transformation with an offset, for each posterior sample (i) appropriately back transformed values will be calculated for each treatment arm, and then (ii) using these back transformed values, the ratio of the treatment arms (All NEMI/All Placebo) will be calculated for each posterior sample, and finally summarised accordingly
 
A comprehensive investigation into a suitable model should be initiated. For example, additional covariates will be investigated such as age, BMI, gender etc.                      Note: when investigating fitting separate statistical models for Lobes (RUL, LUL, RML, RLL and LLL) and Regions (Upper, Lower, Central, Distal and Total), i.e. two models; one for lobes, one for regions. If there are convergence issues an alternative structure of fitting separate statistical models for each Lobe (RUL, LUL, RML, RLL and LLL) and each Region (Upper, Lower, Central, Distal and Total), i.e. ten models; five for lobes, five for regions. a similar model as described in Model Specification should be tested but will include a baseline and a Treatment*Visit term instead of a Baseline*Region term and a Treatment*Visit*Region term, respectively.                      Note: It may also be prudent to investigate a model fitting baseline as a timepoint in which case the log of (or other transformation as appropriate) the absolute results will be analysed in a multivariate model, under a Bayesian framework. The model could include a Treatment*Visit*Region parameter, as well as any co-variates of interest. Note that this model would not include an intercept. The Visit would consist of three levels: Baseline, Day 12 and Day 28, and the Treatment would consist of three levels: Null (when Visit = Screening), NEMI and Placebo. With assumptions as described in Model Specification.
 
An unstructured covariance structure will be used. However, in the event that this model fails to converge, alternative correlation structures may be considered.
 
Models with a Bayesian Framework will use vague priors. If appropriate, conjugate priors will be used. For example, for a multivariate model, the prior for the variance covariance matrix will be an inverse Wishart distribution.
 


Model Results Presentation
 
 
Output from the repeated measures modelling detailed above will be tabulated. In particular, the estimated ratio to baseline (or change from baseline if appropriate), 95% CI, standard error (on the appropriate scale, likely logarithm base e), and posterior probabilities at each time point and for the active treatment comparison with placebo. The scan trimming condition, lung volume and lobe or region description will be included in the outputs.
 

Sensitivity and Supportive Analyses
 
 
It is thought that the use of bronchodilators could affect the HRCT results. The database will contain information on if relief medication was used in the 4 hours prior to each scan, and this
 

information may be used in the sensitivity analyses of the HRCT results including only those who did not take bronchodilator relief medication in the 4 hours prior to HRCT scan.

**Endpoint / Variables**

- Imaging Scan Trimmed endpoints siVaw and siRaw at FRC in the Distal Region only.

**Model Specification**

- It is likely that the data will approximately follow a log normal distribution; however, the most appropriate distribution should be used.
- Separate statistical models will be fitted for each endpoint, i.e. two models; one for siVaw (scan trimmed at FRC in Distal region), one for siRaw (scan trimmed at FRC in Distal region).
- The responses of interest are the change from baseline based on (i) Airways present on scans taken at Screening and Day 12, (ii) Airways present on scans taken at Screening and Day 28, and (iii) Airways present on scans taken at Day 12 and Day 28. The baselines for each of these endpoints are provided in the table below.

	(i) Screening & Day12 Scan trimming	(ii) Screening & Day28 Scan trimming	(iii) Day 12 & Day 28 Scan trimming
Screening Result	✓ (baseline)	✓ (baseline)	
Day 12 Result	✓ (post dose)		✓ (baseline)
Day 28 Result		✓ (post dose)	✓ (post dose)

- The modelling below assumes that the Scan trimming endpoints (Screening&Day12, Screening&Day28 and Day12&Day28) will be analysed in a single multivariate model. This is subject to sensitivity analysis.
- The log of (or other transformation as appropriate) the change from baseline (where baseline is defined in the table above) will be analysed in a multivariate model to account for the correlation between the multiple Scan Trimmings (Screening&Day12, Screening&Day28 and Day12&Day28), under a Bayesian framework. The model will have a separate intercept for each Scan Trimming combination (by fitting a class parameter Scan Trimming, and having no overall intercept), and will also include a baseline\*Scan Trimming and a Treatment\*Scan Trimming parameter. The Visit will consist of two levels: Day 12 and Day 28, the scan trimming will consist of three levels Screening&Day12, Screening&Day28 and Day12&Day28, and the Treatment will consist of two levels: All NEMI and All Placebo. No fixed assumption around the structure of the covariance matrix will be enforced. The priors for the mean vector for each of the parameters (i.e. covariates) will each follow a normal distribution and the prior for the variance-covariance will follow an inverse Wishart distribution. Sensitivity analysis will be conducted to select appropriate parameters for both distributions such that the priors are non-informative with respect to the posterior.
- The change from baseline across the different Scan Trimming pairs (accounting for the average baseline) will be represented via adjusted posterior medians for each of the Treatment Arms, as well as their associated 95% HPD-tailed credible intervals. These results will also be

presented within tabular form, and will be presented after the data have been appropriately back transformed (if applicable).
 
 
The difference between the treatment arms, for the change from baseline across the different Scan Trimming pairs will be represented via adjusted medians, as well as their associated 95% HPD-tailed credible intervals. These results will also be presented in tabular form, and will be presented after the data have been appropriately back transformed to give median ratios (if applicable). For parameters that require a log transformation with an offset, for each posterior sample (i) appropriately back transformed values will be calculated for each treatment arm, and then (ii) using these back transformed values, the ratio of the treatment arms (Active/Placebo) will be calculated for each posterior sample, and finally summarised accordingly.
 
 
The probabilities that the treatment ratio is greater than 1 (for siVaw) and less than 1 (for siRaw), in addition to other values appropriately selected based on the data, will also be computed for each Visit. These results will be presented in tabular format.


Model Checking & Diagnostics
 
 
Model assumptions will be applied, but appropriate adjustments maybe made based on the data. For example if data do not approximately follow a normal distribution then an attempt will be made to find a suitable transformation. Note: Should parameters require a log transformation with an offset, for each posterior sample (i) appropriately back transformed values will be calculated for each treatment arm, and then (ii) using these back transformed values, the ratio of the treatment arms (All NEMI/All Placebo) will be calculated for each posterior sample, and finally summarised accordingly
 
A comprehensive investigation into a suitable model should be initiated. For example, additional covariates will be investigated
 
An unstructured covariance structure will be used. However, in the event that this model fails to converge, alternative correlation structures may be considered.
 
Models with a Bayesian Framework will use vague priors. If appropriate, conjugate priors will be used. For example, for a multivariate model, the prior for the variance covariance matrix will be an inverse Wishart distribution.
 

Model Results Presentation
 
 
Output from the repeated measures modelling detailed above will be tabulated. In particular, the estimated ratio to baseline (or change from baseline if appropriate), 95% CI, standard error (on the appropriate scale, likely logarithm base e), and posterior probabilities at each time point and for the active treatment comparison with placebo. The scan trimming condition, lung volume and lobe or region description will be included in the outputs.
 

Sensitivity and Supportive Analyses
 
 
It is thought that the use of bronchodilators could affect the HRCT results. The database will contain information on if relief medication was used in the 4 hours prior to each scan, and this information may be used in the sensitivity analyses of the HRCT results including only those who did not take bronchodilator relief medication in the 4 hours prior to HRCT scan.
 

### 8.3. Exploratory Efficacy Analyses (From HRCT Analyses)

#### 8.3.1. Endpoint / Variables

To assess the changes in other HRCT parameters such as low attenuation score after once daily repeat inhaled doses of nemiralisib administered to subjects with acute exacerbation of COPD, compared to placebo. Change from baseline for other CT parameters including low attenuation score after 12 days of treatment and after 28 days of treatment.

#### 8.3.2. Summary Measure

The structure of HRCT endpoints is as described in Section 8.2.2, exploratory endpoints include:

- iVlobe
- Percent Predicted iVlobe
- IALD
- LAS
- AT
- BVD
- iVaww
- siVaww

For all endpoints, the data will be inspected prior to analyses to determine whether a data transformation is required. Appropriate transformations will be applied prior to summaries and statistical analyses. It is likely a log transformation will be required for iVlobe, LAS, IALD, BVD iVaww and siVaww, and that no transformation will be required for Percent Predicted iVlobe and AT, however, the most appropriate distribution should be used

Summary statistics will be presented for absolute data and change from baseline. Separate statistical models will be fitted for each scan trimming condition (Untrimmed or Scan Trimmed), lung volume (FRC or TLC) and Regions (Upper, Lower, Central, Distal and Total) combination as appropriate, note: statistical analyses will only be conducted on:

- IALD for upper and lower regions only (within the same model)
- LAS at TLC for total region only
- AT at FRC for total region only
- BVD at TLC for total region only
- siVaww untrimmed data at TLC for distal region only

For the endpoints: LAS, AT and BVD, separate statistical models will be fitted for the Total region only. The change from baseline (accounting for the average baseline associated to the region) will be represented via adjusted posterior medians for each of the Treatment Arms, as well as their associated 95% HPD-tailed credible intervals. These results will also be presented within tabular form, and will be presented after the data have been appropriately back transformed (if applicable). The difference between the treatment arms, for the change from baseline will be represented via adjusted medians, as

well as their associated 95% HPD-tailed credible intervals. These results will also be presented in tabular form, and will be presented after the data have been appropriately back transformed to give median ratios (or median differences if applicable).

For the endpoint IALD, a statistical model will be fitted for both the Upper and Lower regions. The change from baseline across the different regions (accounting for the average baseline associated to the region of interest) will be represented via adjusted posterior medians for each of the Treatment Arms, as well as their associated 95% HPD-tailed credible intervals. These results will also be presented within tabular form, and will be presented after the data have been appropriately back transformed (if applicable). The difference between the treatment arms, for the change from baseline across the different regions will be represented via adjusted medians, as well as their associated 95% HPD-tailed credible intervals. These results will also be presented in tabular form, and will be presented after the data have been appropriately back transformed to give median ratios (or median differences if applicable).

For the endpoint siVaww, a statistical model will be fitted for the distal region using untrimmed data. The change from baseline (accounting for the average baseline associated to the region) will be represented via adjusted posterior medians for each of the Treatment Arms, as well as their associated 95% HPD-tailed credible intervals. These results will also be presented within tabular form, and will be presented after the data have been appropriately back transformed (if applicable). The difference between the treatment arms, for the change from baseline will be represented via adjusted medians, as well as their associated 95% HPD-tailed credible intervals. These results will also be presented in tabular form, and will be presented after the data have been appropriately back transformed to give median ratios (or median differences if applicable).

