#### **8.3.4.1. Statistical Methodology Specification**

For statistical analyses of IALD in the upper and lower regions refer to Section [8.2.4.1](#) for the analysis of untrimmed siVaw but note that it is likely only 1 statistical model would be fitted for the upper and lower regions only. If appropriate this could be adapted into two models; one for upper, one for lower. The probability that the treatment ratio is greater than 1 will be presented for the lower region and the probability that the treatment ratio is less than 1 will be presented for the upper region, in addition to other values appropriately selected based on the data.

For statistical analyses of LAS at TLC in the total region only, refer to Section 8.2.4.1 for the analysis of untrimmed siVaw but note only 1 statistical model would be fitted for the Total regions only. The probability that the treatment ratio is less than 1 will be presented, in addition to other values appropriately selected based on the data.

For statistical analyses of AT at FRC in the total region only, refer to Section 8.2.4.1 for the analysis of untrimmed siVaw however it is likely that no transformation will be required for this endpoint in which case the absolute change from baseline will be fitted and probabilities that the true treatment difference is less than 1, in addition to other values appropriately selected based on the data, will also be computed for each Visit. Note only 1 statistical model would be fitted for the Total regions only.

For statistical analyses of BVD at TLC in the total region only, refer to Section 8.2.4.1 for the analysis of untrimmed siVaw but note only 1 statistical model would be fitted for the Total regions only.

For statistical analyses of siVaww at TLC in the distal region only, refer to Section 8.2.4.1 for the analysis of untrimmed siVaw but note only 1 statistical model would be fitted for the Distal regions only. The probability that the treatment ratio is less than 1, in addition to other values appropriately selected based on the data will be presented.

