13.6.3. Efficacy

HRCT											
Endpoints provided by FluidDA											
Y = Endpoints will be provided by FluidDA.											
	Lobes & Regions										
	LLL	LUL	RML	RUL	RLL	LL	UL	CENTRAL	DISTAL	TOTAL	TRACHEA
iVaw	Y	Y	Y	Y	Y	C	C	Y	C	C	N/A
siVaw	C	C	C	C	C	C	C	C	C	C	N/A
iRaw	Y	Y	Y	Y	Y	C	C	Y	Y	Y	N/A
siRaw	C	C	C	C	C	C	C	C	C	C	N/A
iVlobe	Y	Y	Y	Y	Y	C	C	N/A	N/A	C	N/A
iVlobepred	Y	Y	Y	Y	Y	Y	Y	N/A	N/A	Y	N/A
LAS	Y	Y	Y	Y	Y	Y	Y	N/A	N/A	Y	N/A
IALD	C	C	C	C	C	C	C	N/A	N/A	N/A	N/A
AT	Y	Y	Y	Y	Y	Y	Y	N/A	N/A	Y	N/A
BVD	Y	Y	Y	Y	Y	Y	Y	N/A	N/A	Y	N/A
iVaww	Y	Y	Y	Y	Y	C	C	Y	C	C	N/A
siVaww	C	C	C	C	C	C	C	C	C	C	N/A
Diameter	N/A	N/A	N/A	N/A	N/A	N/A	N/A	N/A	N/A	N/A	Y
Length	N/A	N/A	N/A	N/A	N/A	N/A	N/A	N/A	N/A	N/A	Y
Length/Diameter	N/A	N/A	N/A	N/A	N/A	N/A	N/A	N/A	N/A	N/A	C
C = Endpoints will be Calculated by GSK (see Derived Data below)											
Imaging Endpoints Calculated by GSK											
iVaw LL = iVaw RLL + iVaw LLL											
iVaw UL = iVaw RUL + iVaw RML + iVaw LUL											
iVaw DISTAL = iVaw LL + iVaw UL											
iVaw TOTAL = iVaw CENTRAL + iVaw DISTAL											
iRaw LL = 1/ (1/iRaw RLL + 1/iRaw LLL)											
iRaw UL = 1/ (1/iRaw RUL + 1/iRaw RML + 1/iRaw LUL)											
iVlobe LL = iVlobe RLL + iVlobe LLL											
iVlobe UL = iVlobe RUL + iVlobe RML + iVlobe LUL											
iVlobe TOTAL = iVlobe LL + iVlobe UL											
iVaww LL = iVaww RLL + iVaww LLL											
iVaww UL = iVaww RUL + iVaww RML + iVaww LUL											
iVaww DISTAL = iVaww LL + iVaww UL											
iVaww TOTAL = iVaww CENTRAL + iVaww DISTAL											
siVaw LLL = iVaw LLL / iVlobe LLL											
siVaw LUL = iVaw LUL / iVlobe LUL											
siVaw RML = iVaw RML / iVlobe RML											
siVaw RUL = iVaw RUL / iVlobe RUL											
siVaw RLL = iVaw RLL / iVlobe RLL											
siVaw LL = iVaw LL / iVlobe LL											
siVaw UL = iVaw UL / iVlobe UL											
siVaw CENTRAL = iVaw CENTRAL / iVlobe TOTAL											
siVaw DISTAL = iVaw DISTAL / iVlobe TOTAL											
siVaw TOTAL = iVaw TOTAL / iVlobe TOTAL											
siRaw LLL = iRaw LLL * iVlobe LLL											
siRaw LUL = iRaw LUL * iVlobe LUL											
siRaw RML = iRaw RML * iVlobe RML											
siRaw RUL = iRaw RUL * iVlobe RUL											
siRaw RLL = iRaw RLL * iVlobe RLL											
siRaw LL = iRaw LL * iVlobe LL											
siRaw UL = iRaw UL * iVlobe UL											

$siRaw\ CENTRAL = iRaw\ CENTRAL * iVlobe\ TOTAL$ $siRaw\ DISTAL = iRaw\ DISTAL * iVlobe\ TOTAL$ $siRaw\ TOTAL = iRaw\ TOTAL * iVlobe\ TOTAL$

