$siVaww\ LLL = iVaww\ LLL / iVlobe\ LLL$ $siVaww\ LUL = iVaww\ LUL / iVlobe\ LUL$ $siVaww\ RML = iVaww\ RML / iVlobe\ RML$ $siVaww\ RUL = iVaww\ RUL / iVlobe\ RUL$ $siVaww\ RLL = iVaww\ RLL / iVlobe\ RLL$ $siVaww\ LL = iVaww\ LL / iVlobe\ LL$ $siVaww\ UL = iVaww\ UL / iVlobe\ UL$ $siVaww\ CENTRAL = iVaww\ CENTRAL / iVlobe\ TOTAL$ $siVaww\ DISTAL = iVaww\ DISTAL / iVlobe\ TOTAL$ $siVaww\ TOTAL = iVaww\ TOTAL / iVlobe\ TOTAL$
$IALD\ LLL = 100 * (iVlobe\ LLL\ TLC - iVlobe\ LLL\ FRC) / (iVlobe\ TOTAL\ TLC - iVlobe\ TOTAL\ FRC)$ $IALD\ LUL = 100 * (iVlobe\ LUL\ TLC - iVlobe\ LUL\ FRC) / (iVlobe\ TOTAL\ TLC - iVlobe\ TOTAL\ FRC)$ $IALD\ RML = 100 * (iVlobe\ RML\ TLC - iVlobe\ RML\ FRC) / (iVlobe\ TOTAL\ TLC - iVlobe\ TOTAL\ FRC)$ $IALD\ RUL = 100 * (iVlobe\ RUL\ TLC - iVlobe\ RUL\ FRC) / (iVlobe\ TOTAL\ TLC - iVlobe\ TOTAL\ FRC)$ $IALD\ RLL = 100 * (iVlobe\ RLL\ TLC - iVlobe\ RLL\ FRC) / (iVlobe\ TOTAL\ TLC - iVlobe\ TOTAL\ FRC)$ $IALD\ LL = IALD\ RLL + IALD\ LLL$ $IALD\ UL = IALD\ RUL + IALD\ RML + IALD\ LUL$

Lung Function Parameters
Lung Function Parameters Calculated by GSK

 
FEV1 % Predicted (Men) = 4.30*Height – 0.029*Age – 2.49
 
FEV1 % Predicted (Women) = 3.95*Height – 0.025*Age – 2.60
 
 
Formulas have been taken from Quanjer, 1993 Lung volumes and forced ventilator flows [accessed: 23rd July 2015] where height is measured in metres and age in years at screening.

Rescue Medication Endpoints														
Number of occasions bronchodilator taken in the last 24 per hours 4-week period derived by GSK														

 
Number of occasions bronchodilator taken in the last 24 hours were collected in the daily diary
 
The table below shows which daily diary records are used to calculate the daily diary endpoints for each analysis time period. Any diary data collected in the post-treatment phase of the study will not be slotted.
 
														

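### IALD upper and lower are complements that always add to 100%, yet Section 8.3 models both and gives each its own posterior probability, so Table 2.56 can disagree with itself

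*SAP*

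**What the plan says.** **Definition (SAP 13.6.3).** Each lobe's IALD is its expansion from FRC to TLC as a percentage of total expansion, for example "IALD\ LLL = 100 * (iVlobe\ LLL\ TLC - iVlobe\ LLL\ FRC) / (iVlobe\ TOTAL\ TLC - iVlobe\ TOTAL\ FRC"). The lower region is "IALD\ LL = IALD\ RLL + IALD\ LLL" and the upper region is "IALD\ UL = IALD\ RUL + IALD\ RML + IALD\ LUL". The total volume in the denominator is "iVlobe TOTAL = iVlobe LL + iVlobe UL". Section 8.2.2 recognises no third region: "The endpoint for which only 2 regions (upper & lower) apply is" IALD.

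**Analysis (SAP 8.3.2 and 8.3.4.1).** The plan is to analyse "IALD for upper and lower regions only (within the same model"). A log transformation is called likely, subject to choosing the most suitable distribution. The method is taken from the untrimmed siVaw model in Section 8.2.4.1: log ratio to baseline, a baseline term and a treatment-by-visit term for each region, and an unstructured covariance with an inverse Wishart prior. A fallback is offered: "If appropriate this could be adapted into two models; one for upper, one for lower".

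**Reporting.** "The probability that the treatment ratio is greater than 1 will be presented for the lower region and the probability" of a ratio below 1 is presented for the upper region. Table 2.56 covers both regions. The IALD text nowhere says that the two are complements.

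**The concern.** If lower and upper always add to 100, a rise in one is the same event as a fall in the other. There is one treatment question per visit, but the plan sets up two estimates and two probabilities for it. On the log scale these need not agree, because equal and opposite moves in percentage points are unequal moves in log ratio, and because each region has its own baseline slope. A reader of Table 2.56 could see a fairly high probability in one row and an indifferent one in the other, with nothing to say that both rows describe the same measurement. Where the rows do agree, nothing tells the reader that the second adds no new information.

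**Working it through.** The plan states no figure for IALD to reproduce, so the check starts from its formulas.

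**1. Identity.** From Section 13.6.3, with the sum taken over the five lobes:

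IALD LL + IALD UL = 100 × Σ(lobe TLC − lobe FRC) / (TOTAL TLC − TOTAL FRC).

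TOTAL is LL + UL, which is the same five lobes, so numerator and denominator cancel and the sum is 100. On 10,000 random sets of lobar volumes the largest departure was 6e-13, which is rounding. The fused-lobe rule in Section 13.7.2 does not break the identity. In all five listed patterns the total is missing, so both regions go missing together.

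**2. Asymmetry on the log scale.** From a baseline of 40% lower and 60% upper, a lower ratio of 1.10 means 44% lower. Upper is then 56%, a ratio of 56/60 = 0.933. The two log effects are not mirror images.

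**3. A constructed contradiction.** Take 15 per arm, all starting at 40% lower. On NEMI every subject ends at 39.5%. On placebo seven end at 28%, seven at 52% and one at 40%. The arithmetic means are 39.5 and 40.0, so in percentage points lower is half a point lower on NEMI. With equal baselines the baseline term drops out, and under flat priors each arm's estimate is its mean log ratio:

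| | NEMI | Placebo | NEMI/placebo |
|---|---|---|---|
| Lower, geometric mean ratio to baseline | 39.5/40 = 0.9875 | (28/40)^(7/15) × (52/40)^(7/15) = 0.957 | 1.032 |
| Upper, geometric mean ratio to baseline | 60.5/60 = 1.008 | (72/60)^(7/15) × (48/60)^(7/15) = 0.981 | 1.028 |

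Both shares appear to rise relative to placebo, which is impossible for two parts of 100%. The cause is that spread lowers the mean log ratio in both regions, so a difference in spread between arms moves both rows in the same direction.

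**4. How often.** This part rests on assumptions, because the SAP gives no IALD mean or SD. The 15 per arm is the planned number of completers (Section 2.3). The rest is assumed: lower mean 40-50%, baseline SD 8 points, change SD 2-8 points, true shift 0 or 2 points. The model was a log-ratio ANCOVA fitted to each region.

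- Mean gap between P(lower ratio > 1) and P(upper ratio < 1): about 0.01-0.09. At a 2-point shift it runs from 0.013 (change SD 2) to 0.077 (change SD 8).
- Treatment estimates that move both shares the same way: about 0.2-14% of trials. This is rarest when the shift is large relative to the change SD.

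**5. The joint model.** The plan's first choice fits both regions together. A Bayesian fit with two regions, two visits, unstructured covariance and a vague inverse Wishart prior was run on 60 simulated trials (lower mean 40%, 2-point shift, 15 per arm). The baseline slope was allowed to differ by region and visit, slightly freer than the plan's term. The median gap was 0.07, the 95th percentile 0.25 and the largest 0.35, with 0.29 for lower against 0.63 for upper at the same visit. Joint fitting does not reconcile the rows.

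**6. Other scales.** Untransformed, the two changes have correlation −1 and a covariance determinant of about 5e-13, so the unstructured matrix is singular. On the logit scale, log(lower/upper), the two changes also correlate exactly −1. A single row then gives one answer whichever region is named, but two logit rows in one model would again be collinear.

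**The case against.** **The model is provisional.** The log scale is only likely, Section 8.2.4.1 calls its models current thinking, and it asks for a wider investigation of suitable models. A one-region or logit analysis is therefore open. That is true, but nothing in the text points anyone to it, and the obvious alternative, no transformation, makes the two-region covariance singular.

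**The region layout has a precedent.** Table 2.56 follows the display of an earlier study, and a log(lower/upper) effect is an odds-type measure, which changes what is estimated. This is a fair cost. A footnote alone would deal with double reading of the table but not with the numerical discrepancy.

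**The size is assumed.** This stands, and only ranges are given here. That the rows can disagree follows from the algebra and does not depend on those inputs.

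**Stronger readings that the SAP does not support.** A reader might infer that the plan counts the rows as two independent confirmations. It does not: it puts both regions in one model with free covariance and gives them opposite directions. A reader might also infer that a success decision could flip between rows. The SAP sets no threshold for any posterior probability, so no decision rule is at risk. Nor will Table 2.56 necessarily show shares that fail to add to 100: the model works with ratios to baseline, which are not expected to sum to anything.

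**Conclusion.** The point holds as a limited one. The identity is exact, it follows from the SAP's own formulas, and the missing-lobe rule does not disturb it. The expected analysis therefore answers one question twice, with two numbers that can differ and occasionally contradict each other in direction. Under the stated assumptions the mean gap in probability is about 0.01-0.09 and directional contradiction occurs in about 0.2-14% of trials. These figures are illustrative, since the IALD mean, SDs and shift are all assumed. The consequence is confined to the reading of one exploratory table, 2.56. The primary mRNA analysis and the secondary HRCT analyses are not touched.

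**What to change.** In Sections 8.3.2 and 8.3.4.1:

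- State that IALD upper equals 100 minus IALD lower.
- Model one quantity: the change from Screening in log(IALD LL / IALD UL), or one region only.
- Report one treatment effect and one posterior probability per visit, and derive the upper share as 100 minus the lower.
- Remove the fallback of separate upper and lower models.
- Footnote Table 2.56 that the two regions are complements and represent a single comparison.

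The cost is SAP wording and a simpler model, with no new data. The small downside is that a log(LL/UL) effect is an odds-type ratio and not the region-wise ratio of the earlier study's display. Back-transforming to lower and upper shares by arm for presentation keeps the table readable, and the two shares then add to 100.
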